### 14.2 Original sample size calculation

The following proportions are assumed for each of the individual outcomes as described in section [3.1](#):

- Major congenital malformations: 4.5%
- Perinatal death: 3%
- Neonatal death: 0.9%

[figure not shown]
The probability of the combination of the endpoints is not known in the literature but the proportion of pregnancies with any of the above outcomes will be estimated at 8.2% as described below. This combined probability is computed under the assumption that the individual outcomes are independent.

The primary endpoint is the proportion of pregnancies without any of the above outcomes. The proportions of patients not getting any of the outcomes is assumed to be:

- Major congenital malformations:  $1 - 0.045 = 0.955$
- Perinatal death:  $1 - 0.03 = 0.97$
- Neonatal death:  $1 - 0.009 = 0.991$

None of the outcomes:  $0.955 \times 0.97 \times 0.991 = 0.918$ , i.e. 91.8% of patients are expected not to get any of the pregnancy outcomes above, and  $100\% - 91.8\% = 8.2\%$  are expected to get one of the outcomes.

The sample size calculation is based on the assumption that the proportion of pregnancies without the combined pregnancy outcome is 91.8% in the Levemir® group or the other basal insulin regimens group. The goal is to be able to detect a difference of 3.5% between the proportions without the combined endpoint in the Levemir® group compared to the other basal insulin regimens group. Assuming a maximum 1:2 split between the two groups, a sample size of 1,833 pregnancies is needed in order to have 80% power of achieving significance at 5% level (see [Figure 14-1](#)).

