### 14.3 Revised sample size calculation

A revised sample size calculation has been performed based on a 1:1 split between the number of subjects treated with Levemir® and the number of subjects treated with other basal insulin products and a more realistic pregnancy outcome incidence, while keeping the other assumptions identical to those used in the original sample size calculation.

[Figure 14-2](#) shows the revised sample size calculation based on a 1:1 split between the groups and pregnancy outcome incidences ranging from 92% to 96%. As indicated in the figure, a total sample size of 1222 (based on a 1:1 split including 611 subjects treated with Levemir® and 611 patients on other basal insulin regimens) will be sufficient to be able to detect a difference of 3.5% in the primary endpoint measure when the proportion of pregnancies resulting in none of the 3 pregnancy outcomes is  $\geq 93.5\%$ .

This sample size of 1222 is likely to be sufficient, even if the proportion of pregnancies resulting in none of the 3 pregnancy outcomes, unexpectedly, will be lower than the currently observed (97.3% observed versus 91.8% originally assumed).

**Figure 14-2 Total sample size sufficient to detect a minimal clinically relevant difference of 3.5% for proportion of pregnancies without the combined pregnancy outcome ranging from 92-96% (assuming a 1:1 split between the Levemir® group and the other basal insulin regimens group).**

When calculating the number of subjects to be enrolled in the study, it has to be taken into account that not all subjects will be included from the primary analysis. The percentage of enrolled subjects, which are to be excluded from the primary analysis is approximately 40% and thereby in line with the original assumption used for the sample size calculation. Therefore, the sample size has been adjusted to  $1222 / (1 - 0.40) = 2037$  (as a minimum) subjects to be enrolled in the study.

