#### 14.4 Statistical methods

All endpoints will be analysed on the analysis set.

Continuous variables (maternal HbA1c at start of pregnancy, at the end of each trimester, and height and weight of the infant at 1 year) will be summarised with descriptive statistics (number of observations with available values, number of observations with missing values, mean, 95% confidence interval of the mean, standard deviation, minimum, median, maximum), and categorical variables and Apgar score will be displayed in frequency tables (N, %). The mean of the Apgar score will also be computed.

The primary endpoint, proportion of pregnancies resulting in the combined pregnancy outcome will be computed for the Levemir® group, and for the other basal insulin group, the difference between these proportions will be computed along with the 95% confidence interval and the p-value using Fisher's exact test. This simple analysis might be biased if type of basal insulin is confounded with other risk factors for a negative birth outcome, so to take this into account the primary endpoint will also be analysed using logistic regression, see the description below.

This analysis will be performed for all other endpoints which are proportions, both maternal endpoints, pregnancy outcome endpoints, and infants' endpoints at 1 year of age.

In addition, the primary endpoint will be analysed using logistic regression. Both crude and adjusted models will be performed. The model will include treatment group (Levemir®/other basal insulins group), and adjust for potential confounders such as study site, type of DM, race, hypertension, major hypoglycaemic events during pregnancy, folic acid intake, and use of GLP-1 agonists during pregnancy. Furthermore, HbA1c at start of pregnancy, end of first trimester, and end of second trimester, age and BMI of the woman at baseline, duration of DM, blood pressure and previous foetal pregnancy complications will be adjusted for as appropriate. Adjustments will be performed in a stepwise manner, and further specified in the Statistical Analysis Plan. Similar analyses will be performed for all other endpoints which are proportions for maternal endpoints, or proportions for pregnancy outcome endpoints.

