For the infants endpoints at 1 year of age the proportions will also be analysed using logistic regression, the model will include treatment group (Levemir®/other basal insulins group), study site, race, hypertension, major hypoglycaemic events during pregnancy, folic acid intake, and possible use of GLP-1 agonists during pregnancy as factors. Furthermore, HbA1c at start of pregnancy, end of first trimester, and end of second trimester, age and BMI of the woman at baseline, duration of DM, blood pressure and previous foetal pregnancy complications will be included as covariates. The analyses regarding height and weight will also be adjusted for exclusive and/or partial lactation period.

The means of the continuous endpoints (maternal HbA1c at the end of each trimester and, height and weight of the infant at 1 year), will be compared between the Levemir® group and the other basal insulins group using an analysis of covariance (ANCOVA) model.

The incidence of major hypoglycaemia during pregnancy will be computed for both treatment groups.

Additional exploratory hypothesis-generating analyses may also be performed as deemed relevant.

Differences in gestational age at study entry and exact follow-up time will be taken into account in the statistical analysis where relevant.

All statistical analyses will be performed using appropriate statistical software. All statistical tests will be performed as two-sided tests with a significance level of 0.05.

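### With about 33 primary events expected, Section 14.4 does not say whether the crude test or the adjusted model carries the conclusion, lists more adjusters than the events support, and fixes infant models that the data cannot carry

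*Protocol*

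**What the plan says.** Protocol Section 14.4 gives two analyses of the primary endpoint. The first is the difference in proportions between the Levemir and other basal insulin groups, with a 95% confidence interval and a Fisher's exact p-value. Of this the protocol says: "This simple analysis might be biased if type of basal insulin is confounded with other risk factors for a negative birth outcome". To allow for that, it continues: "In addition, the primary endpoint will be analysed using logistic regression. Both crude and adjusted models will be performed". Neither analysis is labelled primary.

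The adjusters for the primary model are introduced as examples, and some are to be used only where appropriate. Adjustment is to be stepwise, with the rest left to the SAP. Similar analyses are required for the other maternal and pregnancy-outcome proportions.

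The infant text is firmer: "For the infants endpoints at 1 year of age the proportions will also be analysed using logistic regression". It then says outright which factors and covariates the model will include. It has no conditional wording, no stepwise building and no deferral to the SAP.

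Section 14.3 gives the event-free proportion as "97.3% observed versus 91.8% originally assumed".

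**The concern.** Treatment was not randomised, so confounding is the main threat to the comparison, as the protocol itself recognises. If the Fisher test and the adjusted odds ratio disagree, the protocol gives no rule for which one is believed. The sample size was revised for the lower event rate, but Section 14.4 does not weigh its covariate list against the number of events that rate implies. Too few events for the list make adjustment fragile, and selecting covariates from the data may leave out real confounders. In the infant models the covariates are fixed and the events are fewer still.

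**Working it through.** **Inputs (protocol)**
- Analysis size, Section 14.3: "a total sample size of 1222 (based on a 1:1 split including 611 subjects treated with" Levemir and 611 on other basal insulins.
- Event-free proportion, Section 14.3: 97.3% so far, 91.8% originally assumed. The size is said to suffice for a "difference of 3.5% in the primary endpoint measure when the proportion of pregnancies resulting in none of the 3 pregnancy outcomes is" at least 93.5%.
- Power and level, Section 14.2: "in order to have 80% power of achieving significance at 5% level". Section 14.3 carries them over: "while keeping the other assumptions identical to those used in the original sample size calculation". Section 14.4 makes all tests two-sided.

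**The plan's own figure.** Exact enumeration of Fisher's test, 611 v 611, 93.5% v 97.0% event-free, two-sided 5%, gives 79.9% power. The normal-approximation formula gives a total of 1,158 without and 1,270 with continuity correction, either side of 1,222. Enrolment is 1,222 / (1 − 0.40) = 2,037. The sample size therefore reproduces on the crude test.

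**Expected primary events** = 1,222 × (1 − event-free proportion)
- 97.3%: 1,222 × 0.027 = 33.0
- 93.5%: 1,222 × 0.065 = 79.4
- 91.8%: 1,222 × 0.082 = 100.2

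**Terms if every listed adjuster enters the primary model**
- Treatment: 1
- Type of DM, race, hypertension, major hypoglycaemia, folic acid, GLP-1 use: 6
- HbA1c at three time points: 3
- Age, BMI, DM duration, blood pressure, previous foetal complications: 5

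The total is 15, with study site on top. This takes one term per variable; more categories of race, or two blood pressures, would add terms.

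**Events per term, without site**
- Observed rate: 33.0 / 15 = 2.2
- Planning limit: 79.4 / 15 = 5.3
- Original assumption: 100.2 / 15 = 6.7

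For scale only, a conventional 10 events per term (an assumption) would allow about 3 terms with 33 events. Fifteen terms would need 150 events, or 150 / 0.027 ≈ 5,560 pregnancies.

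The protocol does not give the number of sites. If 20 to 50 sites (assumed) entered as fixed effects, the ratio at 33 events would be 33 / (15 + 19) = 0.97 to 33 / (15 + 49) = 0.52.

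**Effect on the treatment estimate.** A simulation (200 runs per setting, assumed true odds ratio 2, no confounding, all terms forced in, 2.7% events) gave extreme or separated coefficients in 43% of fits without site and in 99–100% with 20 or 50 sites. The treatment estimate suffered little: mean odds ratio 2.1–2.2 and 95% interval coverage 94–96%.

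**Infant models at 1 year.** The terms are those above without type of DM: 15 − 1 = 14 including treatment, plus site.
- *Change in a major malformation.* Only affected infants can have one. The whole composite, deaths included, is about 33 at the observed rate, so fewer than about 33 affected infants reach 1 year. Even if half of them changed, the smaller outcome group has at most 16, and 16 / 14 = 1.1 per term before site. With 20 sites (assumed), intercept, terms and site make 1 + 14 + 19 = 34 parameters, more than the infants available. At the planning limit the ceiling is about 79 infants, at most 39 in the smaller group, and 39 / 14 = 2.8 per term.
- *Diabetes.* The protocol gives no rate; a handful of cases is an assumption.
- *Check with assumed inputs.* The specified model failed or separated in every run with 25–30 affected infants, and in 85–100% of runs with about 2–10 events among 1,190 infants.

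**The case against.** The primary model is not fixed. The adjusters are examples, some are conditional, and the SAP is to settle the rest, so covariate choice, penalisation and the handling of site may properly be decided there. The protocol also names the confounding risk itself and pairs the crude test with an adjusted one. The figure of 33 events rests on an interim proportion, and 1,222 is a requirement rather than a cap. The study calls itself exploratory, and the infant endpoints are secondary. All of this stands, and it limits the point.

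A reader might go further and infer that the primary model must carry 15 or more terms, that about half the pregnancies would drop out at event-free sites, or that standard errors would be materially too small. The protocol does not support these readings. The 15 terms are the largest candidate set. Loss of sites needs fixed site effects and a site count, neither of which the protocol gives for the primary model. The simulated coverage of 94–96% shows only mild harm to the treatment estimate. Nor does the protocol call the Fisher test its main analysis or say that it is biased; it says that it might be.

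Two things survive. Deferring covariate details does not settle which analysis carries the conclusion. And the infant wording defers nothing.

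**Conclusion.** The point holds in limited form and should be fixed; it does not invalidate the study.

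- The protocol does not say whether the crude or the adjusted analysis decides the primary question, although it doubts the crude one.
- The full candidate list would leave about 2 events per term at the observed rate and about 5 at the planning limit, before site. This is a reason to shorten the list or adjust differently, not proof that the treatment estimate will be wrong. If stepwise means data-driven selection, which the protocol leaves open, 33 events are a weak basis for it.
- The infant logistic models are wrongly specified as they stand: 14 fixed terms plus site, for outcomes with too few events to support them.

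The primary figures assume 1,222 pregnancies and the stated event-free proportions. The malformation ceiling follows from the same figures. The number of sites, the number of infant diabetes cases and the simulation settings are assumptions.

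**What to change.** 1. Name a confounder-adjusted estimate as the primary analysis and label the crude Fisher comparison descriptive.
2. Size the adjustment to about 33 events, in place of stepwise selection from the full list. One option is a short, pre-specified set of baseline confounders with Firth penalisation and site as a random effect. Another is a propensity score for Levemir against other basal insulin (about 611 per group), with overlap weights and a robust confidence interval. Either is acceptable. If site enters the exposure model, check for sites that prescribe almost only one product. With 33 events, the robust variance is itself a small-sample approximation.
3. Replace the full-covariate logistic models for infant diabetes and change in a major malformation with counts, proportions and exact 95% confidence intervals by group.

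The cost is revised wording in Section 14.4 and the SAP, modest programming and a somewhat wider confidence interval. No data collection changes.

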### **4.2.2 Secondary endpoints**

#### **4.2.2.1 Maternal endpoints**

- Incidence of major hypoglycaemia during pregnancy
- Proportion of pregnancies where the woman experiences at least one major hypoglycaemic event during pregnancy
- Proportion of pregnancies complicated by pre-eclampsia during pregnancy
- HbA1c level assessed as close as possible to conception, end of first trimester, end of second trimester, and at delivery.

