#### 4.2.2.2 Pregnancy outcome endpoints

- Proportion of pregnancies resulting in perinatal death assessed at 1 week after delivery
- Proportion of pregnancies resulting in neonatal death assessed at 4 weeks after delivery
- Proportion of pregnancies resulting in live birth with major congenital malformations and by organ assessed at delivery
- Proportion of pregnancies resulting in live birth with minor congenital malformations and by organ assessed at delivery
- Proportion of induced abortions due to major congenital malformations and by organ assessed at delivery
- Proportion of pregnancies resulting in spontaneous abortion assessed at pregnancy termination
- Proportion of pregnancies resulting in live birth with foetal macrosomia assessed at delivery
- Proportion of pregnancies resulting in live born infants with birth weight > 90th percentile for gestational age and sex (local reference) assessed at delivery
- Proportion of pregnancies resulting in pre-term delivery assessed at delivery

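### Section 14.4 adjusts for hypoglycaemia, GLP-1 agonist use and HbA1c that arise after basal insulin exposure, so the adjusted estimates do not answer the overall safety question

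*Protocol*

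**What the plan says.** Protocol Section 14.4 first compares proportions with Fisher's exact test and concedes that this may be biased if the choice of insulin goes with other risk factors. Crude and adjusted logistic models follow. The adjusted model will "adjust for potential confounders such as study site, type of DM, race, hypertension, major hypoglycaemic events during pregnancy, folic acid intake". A further item on the same list is "use of GLP-1 agonists during pregnancy". It adds HbA1c "at start of pregnancy, end of first trimester, and end of second trimester, age and BMI of the woman at baseline". That second group ends: "blood pressure and previous foetal pregnancy complications will be adjusted for as appropriate". Section 14.4 continues: "Adjustments will be performed in a stepwise manner, and further specified in the Statistical Analysis Plan".

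The model is then extended: "Similar analyses will be performed for all other endpoints which are proportions for maternal endpoints, or proportions for pregnancy outcome endpoints". Those endpoints include "Proportion of pregnancies where the woman experiences at least one major hypoglycaemic event during pregnancy" (Section 4.2.2.1) and "Proportion of pregnancies resulting in spontaneous abortion assessed at pregnancy termination" (Section 4.2.2.2).

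A separate paragraph of Section 14.4 covers the infant endpoints at 1 year. It lists hypoglycaemia in pregnancy, GLP-1 agonist use in pregnancy and HbA1c at all three time points as model terms. It offers them neither as examples nor as appropriate.

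Section 5.4, by contrast, says that confounders and background covariates are gathered at the baseline visit.

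**The concern.** A confounder must be able to influence which insulin a woman takes. Section 13 admits only women whose basal insulin was unchanged from 4 weeks before conception and throughout pregnancy. An event in pregnancy cannot have influenced that choice, but the insulin may have influenced the event. The protocol itself treats major hypoglycaemia and HbA1c in pregnancy as outcomes on which the insulins are compared (Sections 4.1.2 and 4.2.2.1).

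This is a post-authorisation safety study. If an insulin helps or harms the foetus through glycaemic control or hypoglycaemia, a model that holds these constant leaves that part of the effect out. If they share unmeasured causes with the outcome, conditioning on them can also create an association that is not there. The crude comparison does not have this fault, but it is the one Section 14.4 says may be biased.

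**Working it through.** **1. The plan's own figure.** Section 14.3 gives 611 per group for a 3.5-point difference at an event-free proportion of 93.5% or more; 80% power and the two-sided 5% level carry over from Section 14.2. The exact power of Fisher's test with 611 against 611, at 93.5% and 97.0%, is 79.9%, so 1,222 reproduces. Enrolment is 1,222 / (1 − 0.40) = 2,037. Both rest on the crude comparison, so changing the covariate list does not alter them.

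**2. Timing of each variable.**

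| Variable | When it arises | Where stated | Also a compared endpoint? |
|---|---|---|---|
| Basal insulin (exposure) | From 4 weeks before conception, unchanged | Section 13 | – |
| Major hypoglycaemia | During pregnancy, asked at each contact | Section 8.3.8 | Yes |
| GLP-1 agonist use in pregnancy | May predate conception; starting or stopping later is expected | Sections 5.1, 8.3.3 | No |
| HbA1c, end of first and second trimester | During pregnancy | Section 4.2.2.1 | Yes |

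The second and fourth variables come after exposure, the third at least in part.

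**3. What adjusting for a mediator does.** The protocol gives no effect sizes, so these are assumptions: hypoglycaemia in 15% of the comparator group; odds ratio 0.5 for insulin on hypoglycaemia; outcome risk 5% without hypoglycaemia; odds ratio 3 for hypoglycaemia on outcome; no other effect of insulin.
- Outcome risk with hypoglycaemia: odds 0.05/0.95 × 3 = 0.1579, risk 0.1364.
- Comparator: 0.85 × 0.05 + 0.15 × 0.1364 = 0.0630, odds 0.0672.
- Other group: hypoglycaemia odds 0.15/0.85 × 0.5 = 0.0882, proportion 0.0811. Outcome risk 0.9189 × 0.05 + 0.0811 × 0.1364 = 0.0570, odds 0.0604.
- Total-effect odds ratio: 0.0604/0.0672 = 0.90. Adjusted for hypoglycaemia, it is 1.00 by construction.

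A simulation of 2,000,000 records gave 0.89 and 0.99, which agrees within simulation error.

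**4. What adjusting for a collider does.** Here insulin and hypoglycaemia have no effect on the outcome. An unmeasured standard normal factor has a log-odds coefficient of 1.0 on both hypoglycaemia and the outcome, and insulin again has odds ratio 0.5 on hypoglycaemia. The simulated crude odds ratio was 1.00 and the adjusted one 1.08.

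**5. Scale.** At the 97.3% event-free proportion observed (Section 14.3), 1,222 × 0.027 = 33 primary events are expected. Split evenly, the standard error of the log odds ratio is √(2/16.5 + 2/594.5) = 0.35. The 95% interval extends by a factor of exp(1.96 × 0.35) ≈ 2 each way.

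**6. The extension to other endpoints, read literally.**
- *Hypoglycaemia proportion.* The yes/no outcome would also be a covariate. In 1,222 simulated pregnancies (assumed risks 10% and 15%), the crude model fitted normally (odds ratio 0.74 in that sample). The model with the outcome as its own covariate separated completely, with standard errors above 500,000, so it gave no usable treatment estimate.
- *Spontaneous abortion.* The glossary places it before 22 completed weeks. Assuming the second trimester ends later, women with the event generally have no HbA1c from that point. Taking 2,037 pregnancies and a 15% risk (the lower end of the range in Section 3.1), all 276 simulated events lacked the value and the 1,761 complete records held none. Induced abortion, also before 22 weeks (Section 8.3.12), meets the same difficulty.

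**The case against.** The strongest defence is that Section 14.4 leaves the detail open. The confounders are introduced as examples, the HbA1c terms apply as appropriate, adjustment is stepwise, other endpoints get only similar analyses, and the SAP, which is not at hand, is to specify the rest. A reader might infer from the literal text that the hypoglycaemia and spontaneous abortion models cannot be fitted. The document does not support that: nothing obliges the SAP to put a variable in a model it breaks. Nor are all abortions certain to lack the value, because Section 4.2.2.1 takes HbA1c as close as possible to each time point and the protocol sets no window. Pre-eclampsia, macrosomia and neonatal death do not meet the problems in step 6. That part is a literal-reading risk affecting a few endpoints.

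Other points also stand. The protocol does not state that basal insulin type affects hypoglycaemia or HbA1c, so mediation is plausible but not shown. GLP-1 use that began before conception can be a genuine confounder. The shifts in steps 3 and 4 rest on assumed effects and are small beside the imprecision in step 5.

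The defence does not reach the central point. The as-appropriate wording governs the group containing HbA1c, not hypoglycaemia or GLP-1 use, and the infant paragraph has no such wording. Freedom to drop a covariate does not correct a list that calls possible consequences of treatment confounders. Later HbA1c may partly stand in for preconception control, but HbA1c at the start of pregnancy is already listed for that purpose.

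**Conclusion.** The concern holds in this form: Section 14.4 names variables arising after exposure as adjustment variables, and fixes them for the infant endpoints. The adjusted estimate then does not measure the overall effect of basal insulin choice on safety. This conflicts with Section 5.4 on when confounders are collected and with the use of hypoglycaemia and HbA1c as comparative endpoints.

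The size and direction of any distortion cannot be derived from the document. It arises only if insulin type affects these variables; shared causes with the outcome then add collider bias. A reader might infer that a safety difference will be adjusted away; the text shows only that it could be. A reader might also infer a known loss of primary events, since births and deaths between 22 weeks and the end of the second trimester may lack that HbA1c. Each lost event would be 1/33, about 3%, of those expected. But the document gives no count and no complete-case rule, so no total loss can be stated. The crude analyses and the sample size are unaffected.

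**What to change.** In both model paragraphs of Section 14.4, and in the SAP, restrict the main adjusted models to covariates from before conception or the baseline visit that are already collected. Examples are site, diabetes type and duration, race, age, BMI, hypertension and blood pressure at baseline, HbA1c at the start of pregnancy, previous pregnancy complications, folic acid as recorded, and GLP-1 agonist use at conception or baseline.

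Take in-pregnancy hypoglycaemia, later GLP-1 use and end-of-trimester HbA1c out of these models. If wanted, show them in a separately labelled exploratory or mediation analysis, and never for an endpoint they define or one that can occur before they are measured.

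State one limit openly: the baseline visit may be as late as 16 weeks, so even baseline values are taken after exposure began. They are the more defensible choice, not a perfect one.

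The cost is wording only, with no new data and no more patients. The small downside is less adjustment for later glycaemic control in the main estimate.

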### **8.1.5 End of study visit**

The end of study visit will be a 1 year follow-up data collection of the infants to the women with an allowed visit window of +4 months. The follow-up will be performed as a questionnaire sent to the women with infants and will be followed up with a telephone interview of the women with infants. The following information will be asked in the questionnaire:

- Height at the age of 1 year (approximately)
- Weight at the age of 1 year (approximately)
- Duration of exclusive lactation and/or duration of partial lactation (section [8.3.13](#))
- Diabetes in the infants (y/n)
- Changes (progression/regression) of major congenital malformations
- If the infant has experienced any AEs, only ADRs and SAEs should be reported in the eCRF

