### **8.3.11 Pregnancy outcome/Neonatal assessments**

At the delivery visit, the following details regarding the pregnancy outcome/neonate will be recorded in the eCRF:

- Date of birth/outcome
- Time of birth
- Live birth (y/n)
- GW at birth (completed weeks + days)
- Physical examination, including:
  - Length and head circumference at birth (measured in cm with one decimal)
  - Birth weight (measured in grams)
- Gender (male/female)
- Conditions at birth, including

- Apgar score at 5 minutes
- Admission to intensive care unit for more than 48 hours (y/n)
  - Reason
  - Length of stay (days)
  - Treatment

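### The 1-year infant models drop type of diabetes from an otherwise matching adjustment list without giving a reason, and the growth models name neither infant sex nor age at measurement

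*Protocol*

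**What the plan says.** All model statements are in Protocol Section 14.4.

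- **Primary, maternal and pregnancy-outcome proportions.** The logistic model is to "adjust for potential confounders such as study site, type of DM, race, hypertension" and so on. The wording is open, adjustment is stepwise, and detail is left to the SAP.
- **1-year infant proportions.** Here the wording is closed. The model includes treatment group and, as factors, "study site, race, hypertension, major hypoglycaemic events during pregnancy, folic acid intake, and possible use of GLP-1 agonists during pregnancy as factors". A second group of variables ends with "duration of DM, blood pressure and previous foetal pregnancy complications will be included as covariates".
- **Height and weight at 1 year.** Means are compared "using an analysis of covariance (ANCOVA) model". No separate covariate list is given. One sentence adds: "The analyses regarding height and weight will also be adjusted for exclusive and/or partial lactation period".
- **Time.** A general sentence near the end of the section says that gestational age at entry and exact follow-up time are accounted for where this is relevant.

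Type of diabetes is recorded at baseline (Section 8.3.3). Infant sex and date of birth are recorded at delivery (Section 8.3.11). The 1-year data come by questionnaire and telephone, "with an allowed visit window of +4 months" (Section 8.1.5). For the 1-month contact, Section 8.1.4 makes the visit date the date of the body measurements. Section 8.1.5 has no such instruction.

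**The concern.** Basal insulin is chosen in routine care. Section 14.4 itself warns that the unadjusted comparison may be biased by confounding, and Section 5.4 says baseline confounders are collected so that they can be adjusted for. Maternal type 1 versus type 2 diabetes may plausibly be related both to the basal insulin used and to the infant outcomes. One of those outcomes, in Section 4.2.2.3, is diabetes in the infant.

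Because the infant list is closed, an analyst who follows it leaves out a factor that the same section treats as a confounder elsewhere. An analyst who adds it departs from the protocol.

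Height and weight are two of the three key infant endpoints in the summary. They are compared as raw values, although the protocol scales birth weight by gestational age and sex when it defines large-for-gestational-age. Sex and age at measurement are obvious sources of variation in such values, and neither is named for these models.

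**Working it through.** **1. The two lists side by side (Section 14.4).**

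- Primary model, first group: "study site, type of DM, race, hypertension, major hypoglycaemic events during pregnancy, folic acid intake, and use of GLP-1 agonists during pregnancy".
- Infant model, first group: "study site, race, hypertension, major hypoglycaemic events during pregnancy, folic acid intake, and possible use of GLP-1 agonists during pregnancy as factors".
- Second group, both models: three HbA1c values, maternal age and BMI, diabetes duration, blood pressure and earlier foetal complications.

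Type of diabetes is the only variable in the first list that is missing from the second. Infant sex is in neither.

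The infant list is written for logistic regression. The lactation sentence says that height and weight are *also* adjusted for lactation, which implies that the same list carries over to the ANCOVA. This is an inference, not a statement.

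**2. Is there a plan figure to reproduce?** No. The protocol gives no SD, effect size or power for infant growth, and no split of diabetes type by treatment group. Every input below is an assumption except the 611 per group (Section 14.3) and the 4-month window (Section 8.1.5).

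**3. Possible bias from leaving out type of diabetes.**
Bias in SD units = (difference in type 2 share between groups) × (type 1 versus type 2 difference in SDs).

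- Low: 0.05 × 0.1 = 0.005 SD
- Middle: 0.10 × 0.2 = 0.02 SD
- Higher: 0.20 × 0.3 = 0.06 SD
- High: 0.30 × 0.4 = 0.12 SD

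Standard error of a two-group difference = √(2/611) = 0.057 SD, if all 611 per group have 1-year data.

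True rejection rate of a nominal two-sided 5% test = Φ(−1.96 + bias/SE) + Φ(−1.96 − bias/SE).

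- 0.02 SD: ratio 0.35, rate about 6%
- 0.06 SD: ratio 1.05, rate about 18%
- 0.12 SD: ratio 2.10, rate about 55%

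These biases assume that nothing else in the model captures diabetes type, so they sit at the upper end for each pair of inputs.

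**4. Precision cost of leaving out sex.** With equal numbers of boys and girls and a sex difference of d residual SDs, SE inflation = √(1 + d²/4).

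- d = 0.3: √1.0225 = 1.011
- d = 0.5: √1.0625 = 1.031
- d = 0.7: √1.1225 = 1.059

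That is about 1% to 6%.

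**5. Precision cost if age at measurement is also left out.** Suppose age is uniform over 4 months (variance 16/12) and growth is g SDs per month. SE inflation = √(1 + d²/4 + g² × 16/12).

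- d = 0.3, g = 0.1: √(1 + 0.0225 + 0.0133) = 1.018
- d = 0.7, g = 0.4: √(1 + 0.1225 + 0.2133) = 1.156

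That is about 2% to 16%. It applies only if the general follow-up-time sentence is not used for these models, and if measurements really spread over the whole window.

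**The case against.** The strongest reply is that most of this belongs in the SAP, which is not at hand, and that the effects are small or already covered. Several parts of it stand.

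- **ANCOVA.** The printed list is for the infant proportions, and a full covariate list for height and weight is commonly an SAP matter. The omission of type of diabetes is explicit only for the logistic models.
- **Age.** A reader might infer that exact age is simply ignored. It is not: the follow-up-time sentence can naturally be read to cover age at a 1-year measurement. Nor does Section 8.1.5 say that infants are measured at 12 to 16 months. It sets a window for data collection and asks for approximate measurements at 1 year. A false height difference of, say, 1 cm would need assumed growth of 1 cm a month and a full month's difference in mean age between groups, after adjustment for site. Nothing in the protocol suggests that.
- **Sex.** A reader might infer that omitting sex confounds the comparison. Basal insulin must be unchanged from 4 weeks before conception (Section 6.2), so the choice cannot depend on foetal sex. The cost is precision.
- **Residual confounding.** A reader might conclude that the growth comparison is definitely confounded. Diabetes duration, BMI, age, HbA1c, hypertension and blood pressure remain in the model and may absorb part of the type 1/type 2 difference. No imbalance is documented.
- **Lactation.** It is named in addition to the list, not in place of another covariate.

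The dropped factor is not explained by any of this. The open wording and the deferral to the SAP sit with the primary model, not in the infant paragraph.

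**Conclusion.** The point holds in limited form. Section 14.4 removes type of diabetes, without explanation, from a closed list that otherwise repeats the primary model. The infant comparisons may therefore keep some residual confounding by maternal diabetes type. This is certain as a matter of text for the infant proportions and probable for height and weight.

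Its size cannot be known from the protocol. It ranges from negligible to about twice the standard error, and the upper end needs a large imbalance, a large effect and no help from the retained covariates. Omitting sex is a minor loss of precision. On age, the fault is vagueness: the general sentence is not tied to the growth models, and the 1-year visit does not ask for the date of measurement.

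These are secondary endpoints in a study that Section 5.4 calls exploratory. The correction is worth making because it is specific and nearly free.

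**What to change.** In the infant paragraph of Section 14.4:

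- Add type of diabetes to all 1-year infant models, or state why it is left out.
- State that the height and weight ANCOVA uses the same list plus infant sex and exact age at measurement. Age- and sex-standardised scores would be an alternative to the two added terms.

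In Section 8.1.5, repeat the Section 8.1.4 instruction that the date entered is the date of the body measurements.

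The cost is a few sentences, one to three extra model terms and one clarified eCRF date. Type of diabetes, infant sex and date of birth are already collected. The date of measurement at 1 year is not secured by the present text, so that part needs the instruction as well as the model term.
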